Cognitive Training: Subjects are randomly assigned to either active or sham training. Subjects are blinded to assignment. Both groups complete 8 total sessions of training over one month; each session take approximately 30 minutes.

Follow-up Assessment: Subjects complete follow-up Psychiatric and Neuroimaging Assessments. These assessments are identical to the corresponding Baseline Assessments and are designed to assess behavioral and neural response to training.

E2 Due to COVID-19, participants may be contacted via phone and e-mail to participate in some follow-up surveys. Once contacted, we may set up a zoom meeting. A member of the research team will explain that this is completely optional and will review the online survey process with the family over the phone or zoom. If the family agrees to participate, the research team member will e-mail a RedCap survey link that will start with the consent form. Researcher will walk participant through how to complete the surveys over the phone or zoom. Participants will have adequate time to review the consent document and there will be an e-mail address provided if the participant should have any questions. The participants e-signature through REdCap will have a time stamp. After the consent is signed, research staff will send an electronic copy of the signed consent document to the participant via e-mail. Subject Selection and Withdrawal

Subjects will be screened over the phone standardized parent-report psychiatric instruments (Screen for Anxiety and Related Disorders, SCARED; and Mood and Feelings Questionnaire, MFQ).

2.a Inclusion Criteria

We will recruit children between the ages of 7-17 for this study with current separation anxiety disorder, generalized anxiety disorder, and/or social phobia.

2.a Exclusion Criteria

Exclusion criteria include prior diagnoses of ADHD, autism spectrum disorder, intellectual disability (IQ<70), a significant medical problem, or current use of psychotropic medication other than SSRIs (children who are currently taking an SSRI and are still experiencing symptoms of anxiety will not be exluded).

2.b Ethical Considerations

There are no major ethical concerns associated with this study.

2.c Subject Recruitment Plans and Consent Process

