Children will be recruited through local schools, pediatricians' offices, and through [name] child anxiety clinic by asking staff to present IRB approved recruitment materials to potentially interested families. We will also recruit with advertisements, press releases, websites, and placement of approved flyers and materials throughout the greater Washington University community as well as throughout the St. Louis community.

A member of the research team will review screening materials and contact potential participants by phone. This member of the research team will provide parent participants with information about the study and required elements of consent over the telephone prior to obtaining the parent's verbal consent to participate in the screening elements of the study (Initial Phone Screen as well as SCARED/MFQ). After obtaining verbal consent, a research assistant will administer the Initial Phone/Exclusion Screen to all potential participants. If a parent and child meet eligibility criteria for enrollment in the study based on their Initial Phone Screen, and parents indicate they wish to continue with the study, the research team will arrange an in-person assessment. On the day of the in-person assessment, a research assistant will provide ample time for the parents to read/review the consent form and will answer any questions the parent may have prior to signing.

2.d Randomization Method and Blinding

Subjects will be randomized to active vs. sham treatment on a 50/50 basis. The participants and the staff performing the pre- and post- treatment psychiatric interviews will remain blinded throughout the study. Study staff administering the treatment will be aware of the active vs. sham status of the participant, in order to deliver and monitor the appropriate cognitive training program.

2.e Risks and Benefits

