Active training: In between the presentation of the cue and target, three "distractor" boxes appear at irrelevant locations at random times. Subjects are instructed to ignore these boxes. It is the active ignoring of these boxes, while maintaining attention voluntarily at the cued location that is proposed to reduce subjects' stimulus-driven attention and reduce excessive VAN activity. **Sham training:** Subjects perform the same

number of trials, of the same task, with the exception that the "distractor" boxes never appear. Thus, subjects still have to voluntarily direct attention, but they do not get practice ignoring irrelevant distractors. Both subjects and clinical interviewers will be

blinded to active versus sham treatment. Subjects will be randomized to treatment arm.

3.b Treatment Regimen

Half of the subjects will be randomized to active cognitive training and half will be randomized to sham training. Children will participate in 8 total 30-minute training sessions, twice a week for 4 weeks.

3.c Method for Assigning Subjects to Treatment Groups

Subjects will be randomized to active vs. sham treatment on a 50/50 basis.

3.d Subject Compliance Monitoring

Subjects will be participating in the cognitive training program twice a week for four weeks in the presence of a trained research assistant.

3.e Blinding of Study Drug

Subjects will not be aware if they are participating in the active or sham treatment.

F Study Procedures

F1 Screening for Eligibility

Subjects will be screened over the phone standardized parent-report psychiatric instruments (Screen for Anxiety and Related Disorders, SCARED; and Mood and Feelings Questionnaire, MFQ).

F2 Visit 1

Child/Parent In-Office Assessment:

Parents will begin by completing Kiddie Schedule for Affective Disorders and Schizophrenia Present and Lifetime Edition (K-SADS-PL), the Pediatric Rating Scale, (PARS), and the Family Interview for Genetic Studies (FIGS) with trained research staff. These semi-structured interviews will be audio taped and will only be listened to by study staff. Parents will also complete additional questionnaires. The child will participate in a computer game that is designed to test various aspects of their attention.

The child will rest their chin on a chin rest and their eye movements will be recorded. There are three different versions of the game. In each version, the computer game involves looking at a central "+" sign and pressing a button when a target appears in

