The primary outcome will be reduction in symptoms of anxiety as measured by the SCARED in study Phase 2. Total SCARED scores at sessions 2, 4, 6, and 8 will be subtracted from the baseline SCARED score, yielding a delta SCARED score for each

visit. These data will be analyzed with a mixed random effects repeated-measures model. In this model, time, treatment (active versus sham), and time x treatment interaction are fixed effects; baseline SCARED scores and subject within treatment are random effects; and delta SCARED scores are the dependent variable. Our hypothesis predicts a significant time x treatment interaction, with a greater decrease in anxiety from pre- to post- training in the active relative to the sham group. Secondary outcomes will include symptoms of anxiety on the PARS and diagnostic status.

We will test whether active versus sham training significantly reduces symptoms in children with anxiety disorders. The primary outcome will be reduction in symptoms of anxiety as measured by the PARS. We will perform a 2 x 2 ANOVA with treatment arm (active versus sham) and time (pre- versus post-training) as effects of interest.

G4 Missing Outcome Data

We will use an intention-to-treat analysis and carry the last observation forward. Because this is a pilot study, we will also compare active versus sham treatment among completers in a follow-up analysis.

G5 Unblinding Procedures

The principal investigator will be made aware of each subject's assignment after that subject has completed all study procedures including post-treatment psychiatric assessment.

H Data Handling and Record Keeping

H1 Confidentiality and Security

Telephone conversations about the study, the consent process, and all portions of the study will take place in a private office. All subjects will be marked with a random identification number so names will not be recorded on any of the data. All data will be stored in locked filing cabinets and on password protected computers. Also, only the research team will have access to study information. Participants can refuse to answer any questions and withdraw from the study at any time.

H2 Training

All current study staff have extensive experience in study procedures, based on similar prior studies performed in the lab. Any new personnel will be trained by current study staff.

H3 Case Report Forms and Source Documents

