All data will be labeled with a number and not the participant's name. All electronic data will be stored in a locked cabinet and on password protected and encrypted data storage devices/computers. Paper/hard copy records will be stored in a locked filing cabinet in a

locked room.

H4 Records Retention

All data will be retained and destroyed once the study is completed.

Study Administration

I1 Organization and Participating Centers

National Institutes of Mental Health, Bethesda, Maryland & Washington University School of Medicine, St. Louis, MO

12 Funding Source and Conflicts of Interest

Institutional Grant/Award: FBJH/ICTS

Federal Agency: NIH, National Institute of Health

ATTENTION AND RELATED FUNCTIONAL BRAIN NETWORKS IN PEDIATRIC

ANXIETY DISORDERS

There are no conflicts of interest.

13 Subject Stipends or Payments

Caregivers and child will be paid a total of \$25 an hour together for each in person assessment, \$50 for the completion of the cognitive training, and an additional \$25 per hour for neuroimaging sessions.

Caregivers and child will be paid a total of \$50 for completion of the follow-up surveys on a Forte Card.

14 Study Timetable

Our goal is to randomize 90 subjects to active versus sham treatment over 18 months at two sites (Washington University and the National Institute of Mental Health). To achieve, this goal we will recruit, on average, 2.5 subjects per month per site. The current plan is to perform this study from January 2018 through June 2019.

J Publication Plan

Manuscripts reporting the primary outcome of the study as well as the neural effects of training will be written at the completion of the study.

K Attachments

K1 Informed consent documents

Novel Treatment Study Assent

Novel Treatment Study Imaging Assent

Novel Treatment Study Imaging Consent

Novel Treatment Study Informed Consent

Novel Treatment Consent for Phone Screen

K2 Questionnaires or surveys

Screen for Anxiety Related Disorders (SCARED)

Mood and Feelings Questionnaires (MFQ)

Kiddie Schedule for Affective Disorders and Schizophrenia Present and Lifetime Version(K-SADS-PL)

Childhood Depression Inventory (CDI)

Attention General Questionnaire

Contact Information Sheet

Pediatric Anxiety Rating Scale (PARS)

Pubertal Development Scale (PDS)

Family Interview for Genetic Studies (FIGS)

Conners

L References

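### The principal investigator is unblinded child by child during accrual, so study conduct and unsettled analysis choices could be made with by-arm results in view

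*Combined protocol and SAP*

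**What the plan says.** G5 (Unblinding Procedures) reads: "The principal investigator will be made aware of each subject's assignment after that subject has completed all study procedures including post-treatment psychiatric assessment". No other section delays or limits this release.

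Section 2.d (Randomization Method and Blinding) lists who is protected for the whole study: "The participants and the staff performing the pre- and post- treatment psychiatric interviews will remain blinded throughout the study". The principal investigator is not on that list. The same section says that the staff who deliver training know each child's arm, because they have to run the right program. C1 describes the trial as a double-blind pilot.

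The Study Timetable gives the accrual plan: "Our goal is to randomize 90 subjects to active versus sham treatment over 18 months at two sites", and "we will recruit, on average, 2.5 subjects per month per site". Section 3.b gives the length of training: "Children will participate in 8 total 30-minute training sessions, twice a week for 4 weeks". Visits 1 and 2 come before training, and visits 11 and 12 after it.

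Three further places bear on the point:
- G2 describes no interim analysis, monitoring board or statistical stopping rule.
- H1 limits access to study information to the research team and sets no barrier within that team.
- G3 opens with "The primary outcome will be reduction in symptoms of anxiety as measured by the SCARED in study Phase 2", analysed by a mixed model. Its next paragraph names PARS as primary, analysed by a 2 x 2 ANOVA. C1 also names PARS.

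**The concern.** A rule triggered by each child's own completion gives the principal investigator a growing list of assignments during accrual. If this role also sees outcome data, which the document does not prevent, the two together amount to an unplanned look at the comparison by arm.

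Two things would then be exposed. One is conduct: decisions on recruitment, continuation, withdrawals and supervision of blinded staff could be coloured by emerging results. The other is analysis: G3 leaves the primary outcome and its model unsettled, and anyone resolving that conflict with arms known could not show that the choice was made blind. The document gives no reason for releasing assignments early, so the double-blind description is weakened for no stated gain.

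**Working it through.** **Inputs from the document.** Accrual is 2.5 children per month per site at 2 sites for 18 months, with a target of 90. Training lasts 4 weeks, with two visits before and two after.

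**Assumptions.** Accrual is uniform. The lag L from enrolment to a child's last visit is not stated. Training alone takes about a month, so L is taken as 1 to 3 months.

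**Step 1: reproduce the plan's figure.** 2.5 x 2 = 5 children per month, and 5 x 18 = 90. This matches the target. The planned dates ("The current plan is to perform this study from January 2018 through June 2019") also span 18 months.

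**Step 2: assignments already released when the last child enrols.** Number known = 5 x (18 - L). At mid-accrual (month 9) it is 5 x (9 - L). Children enrolled after the first release = 90 - 5 x L.

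| Lag L | Known when last child enrols | Known at month 9 | Enrolled after first release |
|---|---|---|---|
| 1 month | 5 x 17 = 85 (94%) | 40 | 85 |
| 2 months | 5 x 16 = 80 (89%) | 35 | 80 |
| 3 months | 5 x 15 = 75 (83%) | 30 | 75 |

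More assignments are released between the last enrolment and the last child's own assessment.

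**Step 3: what those assignments would show if joined to outcomes.** With equal information per child, a comparison on a fraction t of the children correlates with the final one by the square root of t. For 85, 80 and 75 of 90 this gives 0.97, 0.94 and 0.91. A by-arm tabulation at that stage would nearly show the final result. This describes what would be visible; the document does not say that anyone makes such a tabulation.

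**Step 4: who knows the arm, and when.**
- Participants and psychiatric interviewers: blinded throughout (2.d).
- Training staff: aware from the start (2.d).
- Principal investigator: told child by child after completion (G5).
- Analyst: not mentioned.
- Outcome data: open to the research team, with no stated restriction on the principal investigator (H1).

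**Step 5: after the fix.** With release held to database lock, the number known to the principal investigator when the last child enrols falls from 75-85 to 0 of 90.

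**The case against.** The strongest reply is that the safeguards that matter most are in place. A child's arm is released only after that child's own post-treatment assessment. PARS is rated by interviewers who stay blinded, and SCARED is completed by children and parents. The principal investigator is not shown to rate, enrol or treat anyone; screening and consent are assigned to other research staff. This stands, and it means that G5 does not directly unblind any rating. Whether past arms help to predict the next one cannot be judged either, because no block size or concealment method is given.

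A second reply is that training staff know every arm from day one, and that the fix leaves this untouched. That is true, but they need the knowledge to deliver the program. The document gives no such reason for the principal investigator.

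A third is that the primary outcome is less open than it looks: C1, C3 and the second paragraph of G3 all point to PARS, and the SCARED sentence refers to a study phase that is not otherwise described. This narrows the choice without closing it, because the first paragraph of G3 makes PARS secondary.

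Three stronger readings are tempting and not supported:
- *The study is run and analysed with by-arm results in view.* G5 releases assignments. The document does not say that this role tabulates outcomes by arm or makes the analysis choices. It only leaves both possible.
- *G5 inflates the false-positive rate by a known amount.* The inflation from picking the better of two outcomes comes from G3 naming two. It would be the same if everyone stayed blinded until lock and the better one were then chosen, so it does not measure the effect of G5.
- *The later surveys are collected after unblinding.* E2 says that "participants may be contacted via phone and e-mail to participate in some follow-up surveys". Whether these optional surveys count among the procedures that must be complete before release under G5 is unclear, and G3 gives them no outcome role.

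**Conclusion.** The point holds as a weakness in blinding safeguards. G5 permits rolling release to the principal investigator, and the plan's own accrual rate puts about 75 to 85 of 90 assignments (83% to 94%) in this role's hands when the last child enrols. That range rests on uniform accrual and an assumed lag of 1 to 3 months. With no barrier to outcome data, no planned interim analysis and two named primary outcomes, conduct and analysis decisions could be made with by-arm results in view. The size of any resulting bias cannot be derived from the document, and no rating is shown to be compromised.

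The version is dated 12/10/2020, after the planned end of June 2019, and the conflict in G3 is still there. If the timetable was kept, assignments were released before the primary outcome was settled in the text. The document does not say whether it was kept.

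**What to change.** Rewrite G5 so that the principal investigator, the outcome interviewers and the analyst stay blinded until all three of these conditions are met:
1. The last randomised child has completed the final study assessment, meaning visit 12 and any follow-up survey that will be analysed by arm.
2. The database is locked.
3. The analysis plan, with one primary outcome, is signed.

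Until then, only the training staff and the holder of the allocation list know assignments. Any earlier unblinding of an individual is logged with its reason. Add the principal investigator and the analyst to the list in 2.d so that the two sections agree.

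If assignments have already been released, record when, and record when the primary outcome was fixed, so that a reader can see which came first.

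The cost is a short text change. The downside is that the principal investigator cannot learn or share a child's arm until the end of the study.
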